1.0 LIST OF ABBREVIATIONS

Abbreviation	Full Name
AUC	Area under the curve
BPI	Brief Pain Inventory
CTN	Clinical Trials Network
LI	Lead Investigator
NS Metric	Narcotic Score Metric
OVN	Ohio Valley Node
OUD	Opioid use disorder
OESW-D	Overdose Experiences, Self and Witnessed-Drug
PHQ-2	Patient Health Questionnaire-2
PDMP	Prescription Drug Monitoring Program
POMI	Prescription Opioid Misuse Index
POUD	Prescription opioid use disorder
ROC	Receiver operating characteristic
SF-12	Short Form-12
TAPS	Tobacco, Alcohol, Prescription medication and other Substances
WHO ASSIST	World Health Organization Alcohol, Smoking, and Substance Involvement Screening Test

2.0 STUDY SYNOPSIS

2.1 Study Objectives

Using opioid therapy to treat pain effectively, while minimizing potential adverse consequences, is an important goal. Appriss Health has developed the “Narcotic Score,” referred to as the “NS metric” hereafter, which uses Prescription Drug Monitoring Program (PDMP) data on opioid and sedative prescriptions and aberrant drug behavior (e.g., multiple providers, pharmacies, etc.) to compute a score quantifying the extent of the patient’s risk for opioid-related adverse events in relation to all prescription opioid users. The association between the NS metric and other indicators of opioid use or risk has not been evaluated, and hence, the degree to which this metric is a useful clinical screening tool is unknown. In addition to the NS metric, the Tobacco, Alcohol, Prescription medication and other Substances (TAPS) tool is rapidly becoming recognized as a high-quality substance use screening measure for outpatient health care settings. Given the somewhat limited opioid-using sample in the TAPS tool validation study ($\leq 5\%$ for prescription opioids; $< 4\%$ for heroin¹), the current study provides the opportunity to (1) to better assess the validity of the TAPS Tool as it would be used in clinical practice in community pharmacy settings (including rural locations), and (2) to provide more clinically useful information for the use of the TAPS Tool by community pharmacists. The present study has two objectives:

- 1) Evaluate the concurrent validity of the NS metric as a clinical measure of high risk opioid use and establish clinically useful risk-level thresholds relative to the widely validated gold standard of the World Health Organization Alcohol, Smoking, and Substance Involvement Screening Test (WHO ASSIST).²
- 2) Collect TAPS tool data in a large sample of individuals filling opioid pain medications to facilitate further validation of this instrument with the WHO ASSIST.

2.2 Study Design

This study is a one group, cross-sectional, health assessment study. Participants who enroll in the study will complete on-line surveys of opioid utilization and risk, overdose history, substance use, mental health, and physical health at a single time point. Appriss Health will provide NS metric scores for all participants. These data will also be used to 1) validate and to identify clinical cut-off values for the NS metric and 2) to further validate the TAPS tool.

2.3 Study Population

Approximately 1,523 patients will be recruited from approximately 15 community Kroger community pharmacies. Trained pharmacy staff will inform potentially eligible participants, or individuals receiving at least one prescription(s) for potentially eligible participants, of the survey opportunity. Interested patients will complete an encrypted electronic “interest survey,” which will trigger REDCap to email the patient a link to a secure web-portal containing e-consent (i.e., an electronic information sheet that is submitted by participants indicating their consent to participate in the study) and self-screening assessment forms. Following submission of the e-consent and successful qualification on the self-screening assessment, the health survey will be made available to participants for completion. The REDCap audio features will be enabled to allow participants with any reading difficult to request specific items be read out loud.

2.4 Assessments

The key assessments are: 1) The NS metric, obtained from Appriss Health, which is a continuous indicator on a 000-999 scale (higher scores indicate increased risk for adverse opioid-related

outcomes);^{3,4} 2) The WHO ASSIST; and (3) the TAPS Tool. The WHO ASSIST and TAPS Tool will be completed by participants through a secure REDCap-hosted web portal. Other assessments to be captured via self-report through the secure REDCap-hosted web portal include: 1) opioid medication misuse assessed with the Prescription Opioid Misuse Index (POMI);⁵ 2) pain severity assessed by the Brief Pain Inventory (BPI);⁶ 3) general health status measured with a 1-item subscale from the Short Form (SF)-12;⁷ 4) depression assessed with the Patient Health Questionnaire (PHQ)-2;⁸ and 5) overdose frequency history assessed using the Overdose Experiences, Self and Witnessed (OESW-D)—Drug instrument.⁹

2.5 Analyses

A series of *a priori* analyses will be conducted to evaluate the validity of the NS metric relative to the widely validated gold standard WHO ASSIST and to identify cutoff thresholds. *A priori* analyses will involve conducting Receiver Operating Curve Analyses (ROC; i.e., sensitivity and specificity, area under the curve [AUC]) to identify clinical cutoff values for the NS metric and low, moderate, and high WHO ASSIST scores. We will also conduct correlational, regression, and Cohen's Kappa statistical analyses to evaluate the relationship between the NS metric and the WHO ASSIST.

We will also conduct *exploratory* correlational and regression, and Cohen's Kappa statistical analyses to validate the relationship between the NS metric and measures of opioid medication misuse as well as history of opioid overdose. Exploratory ROC, correlational, regression, and Cohen's Kappa statistical analyses between the WHO ASSIST and the TAPS Tool will also be conducted.

3.0 STUDY SCHEMA

- Adult patients at participating Kroger Pharmacies in Ohio and Indiana will be approached while picking up qualifying opioid medications
- Pharmacy staff shares details of study
- Persons picking up medications for others will receive a study flyer with instructions on how the opioid recipient may remotely complete the interest form

- Patient inputs contact information into REDCap interest form
- Patient receives email link to e-consent and self-screening assessment

- Upon successfully qualifying on the self-screening assessment and completing the e-consent, the health assessment survey is made available to the participant

- Participant completes survey, which includes:
 1. WHO ASSIST
 2. POMI
 3. TAPS Tool
 4. OESW-D
 5. PHQ-2
 6. SF-12 (general health subscale)
 7. BPI
 8. Demographics

- Ohio Valley Node (OVN) staff verifies the participant has not previously completed the survey and, if verified, sends participant \$50

- Data are checked for completeness, stored in HIPAA compliant environment, and merged regularly with NS metric
- Final merged dataset with NS scores and health assessments are shared with OVN and University of Utah
- Data are analyzed and results are reported

4.0 BACKGROUND AND RATIONALE

4.1 Background

The US opioid epidemic continues to have serious public health ramifications. In 2017, nearly 11.1 million individuals in the US reported misuse of opioid pain-relievers in the past year,¹⁰ with approximately 36% obtaining opioid medications for misuse through filling medications from a prescriber.¹⁰ A robust literature in the last decade has documented a clear trajectory for individuals who begin with opioid medication misuse transitioning to heroin use.¹¹⁻²² In 2017, over 650,000 individuals in the US reported past-year heroin use.¹⁰ Fatal overdose deaths involving prescription opioids, heroin, and synthetic opioids has continued to increase across the US—continuing to increase in 35 states from 2013-2017.²³ Given these persistent trends for adverse opioid-related outcomes in populations across the US, it is critical to work to identify those who are at risk, deliver appropriate care that will help prevent progression to more severe opioid-related outcomes, and provide referral and treatment resources to those who suffer from opioid use disorder (OUD). Therefore, it is necessary to expand the continuum of care to health care settings that previously may have been underutilized.

One underutilized resource for addressing the current opioid epidemic is community pharmacies. In the US, 93% of individuals live within 5 miles²⁴ of the >60,000 community pharmacies that employ >170,000 pharmacists.²⁵ National data show that >40% of community pharmacies have private counseling rooms where pharmacists can discretely and confidentially provide care.²⁶ Pharmacists are ranked among the top 2 most trusted professionals in the US,²⁷ with research showing patients are willing to receive behavioral health information from these professionals.²⁸

Previous research among pharmacists has further provided support for possible identification and intervention by community pharmacists for opioid misuse among patients. Results of a survey in 2 states (N=739) about opioid medication misuse and possible screening and intervening found that most pharmacists (90%) wanted to help patients who misuse opioid pain medications but reported needing training (81%) and tools (80%) to effectively do so.^{29,30} Furthermore, results from 333 patients (response=71.2%) screened in 4 community pharmacies receiving opioid medications found opioid medication misuse among 15% of patients.³¹ Among those with misuse, 98% had ≥ 1 comorbid health condition known to increase risk for misuse or overdose, including depression, posttraumatic stress, risky alcohol use, and poor health and pain exceeding US norms. Patients in this sample were agreeable to pharmacists screening their opioid medication use (70.9%) and discussing medication use if pharmacists had a concern (82.1%; with no differences between misusing and non-misusing respondents, $p>.05$).^{32,33} Given this important foundation for the expansion of the role of community pharmacy to address the opioid epidemic, it is critical to identify opportunities to better equip these health care professionals with tools to identify patients who are at risk for opioid-related adverse events.

The most important clinical tool pharmacists have available to identify possible misuse of opioid medications is prescription drug monitoring programs (PDMP),³⁴⁻⁴¹ which capture patient-level prescription dispensing information to inform monitoring, dispensing decisions, and possible intervention.^{35,36,38,41} These tools are available in all US states (Missouri relies on a county-administered program) and have the potential to enable pharmacists to identify patients at-risk for opioid-related adverse events, such as addiction and overdose. Appriss Health is the largest PDMP platform vendor in the US, providing PDMP services statewide in 42 states, with approximately 1 million users. The Appriss platform facilitates PDMP data sharing in 44 states and captures 8 million monthly transactions. PDMP programs, such as the Appriss platform, have demonstrated clear results for reducing opioid prescribing.³⁵⁻⁴¹ PDMP effectiveness has not been clear on substance use outcomes,³⁸ including rates of overdose.⁴²⁻⁴⁴ PDMP output data are limited

in clinical utility, do not provide decision support, and thus users must act on “best judgment” to provide patient care and referrals with a limited evidence base. Appriss Health has developed an opioid risk measure, the NS metric, which could support community pharmacists’ decision-making regarding interventions for opioid risk. However, the validity of the NS metric has not been evaluated.

4.2 Rationale

In light of the continued escalation of the opioid epidemic nationally, combined with the promising opportunities afforded by the further inclusion of community pharmacy settings for engaging patients with opioid-related risk, it is important to evaluate whether current PDMP risk metrics correlate with clinically validated opioid risk tools and if clinically meaningful risk cutoffs exist for PDMP risk metrics. The present study will accomplish two important objectives.

First, the NS metric has not been empirically validated with standardized opioid risk tools. This formative research project will leverage public/private partnerships among the OVN, University of Cincinnati, University of Utah, Purdue University, Appriss Health, and Kroger Pharmacies to validate and identify risk thresholds for the NS metrics through comparison with the widely validated gold standard WHO ASSIST. Successfully completing this objective is the first important step in understanding the validity of current PDMP metrics and establishing clinically meaningful risk tools for opioids, which would allow community pharmacists to accurately and rapidly triage patient opioid risk. These results will provide foundational data that will allow our team to continue this line of research and further collaborate with Appriss Health to identify and test a PDMP-based, opioid-focused, decision support tool for community pharmacies.

The second objective of this study is to further validate the TAPS tool. Mentioned previously, the TAPS tool is rapidly becoming recognized as a high-quality substance use screening measure for outpatient health care settings.¹ The recent validation study for this tool, conducted with primary care patients, showed high levels of sensitivity and specificity for tobacco and heavy alcohol use (≥ 0.79), and adequate sensitivity and specificity for illicit and prescription drug use (≥ 0.63).¹ Given the somewhat limited opioid using sample in the validation study ($\leq 5\%$ for prescription opioids; $<4\%$ for heroin¹), the current study provides the opportunity (1) to better assess the validity of the TAPS Tool as it would be used in clinical practice in community pharmacy settings (including rural locations), and (2) to provide more clinically useful information for the use of TAPS Tool by community pharmacists.

4.3 Significance to the Field

The first study objective builds on previous research from our team that has focused on understanding the needs and opportunities available for identification of, and intervention for, problematic opioid use among community pharmacy patients prescribed opioid medications.^{29,30,45-47} The results of this project stand to meet several important needs of community pharmacy to increase their involvement in the identification of patients at-risk for opioid-related adverse events, such as addiction and overdose. Specifically, if the first objective is achieved, the results from this study would enable rapid identification of opioid-related risk utilizing data from a widely-available PDMP platform vendor (Appriss Health).

The second study objective also builds on previous research from CTN investigators^{1,48} and stands to extend the knowledge base in the field regarding the utility of the TAPS Tool as a universal substance use screening instrument for outpatient clinical care settings.

5.0 OBJECTIVES

5.1 Primary Objective

The primary objective of this project is to validate and identify low, moderate, and high risk thresholds for the NS metric through comparison to the widely validated gold-standard WHO ASSIST measure for opioid use risk in adult community pharmacy patients dispensed opioid medication therapies.

5.2 Secondary objective

The secondary objective of this study is to collect data to further validate the TAPS Tool. This measure will be compared to the WHO ASSIST in a novel sample of adult outpatients from community pharmacies with active opioid medication prescriptions.

6.0 STUDY DESIGN

6.1 Overview of Study Design

We will implement a one-time, cross-sectional, self-administered, health survey among eligible adult patients dispensed opioid medications from 15 participating Kroger pharmacies in Ohio and Indiana. This design will accomplish the purpose of the study given that it will allow for recruitment of a sample of patients with sufficient power to identify and validate clinical threshold values for the NS Metric. Patients recruited will complete a series of validated measures to assess opioid use and risk behaviors, substance use, and physical and mental health.

Study survey data will be merged on a regular basis with the NS metric by Appriss Health and shared with OVN and University of Utah investigators for assessment of data quality and to conduct statistical analyses. See section 11.9 for an overview of Data Quality Assurance. Appriss Health will deterministically match and merge the survey data with the NS metric using patient contact information (e.g., name, address, phone number) as well as information regarding the location of the pharmacy and time/dates for when the study interest form was completed and submitted into REDCap.

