### **3.5 STATISTICAL METHODS**

The Completer Population will be randomly split into training data set and testing data set with a 1:1 ratio, stratified by WHO ASSIST risk levels. The training data set will be used to select cut-points for NS metric risk levels, and testing data set will be used to address statistical Aim 2, validating the selected cut-points. The proposed approach allows us to assess the predictive ability of the NS metric classifier with an independent testing data set and avoid potentially overfitting. All analyses will be performed both overall and within sex specific subpopulations, to examine sex difference in discrimination, selected cut-points, and agreement between measures.

Summary statistics will be provided for the following clinical assessments for the population, by gender subpopulation, by pharmacy recruitment sites.

- NS Metric
- WHO ASSIST
- TAPS
- OESWD
- Prescription Opioid Misuse Index
- PHQ-2
- SF-12
- Brief Pain Inventory

**Statistical Aim 1 – To assess the ability of NS metric to discriminate between opioid use risk groups and to determine cut-off points for NS metric total score.**

*To assess the ability of NS metric to discriminate between opioid use risk groups:*

The discriminative validity of an instrument concerns its ability to discriminate between known groups. In the project, the known groups are the low risk, moderate risk, and high risk groups as defined by WHO ASSIST opioid domain (0-0.5 range=low risk, 0.5-14.5 range=moderate risk, and 14.5-20 range=high risk).

A receiver operating characteristics (ROC) analysis will be conducted to 1) assess the overall discriminative ability of NS metric score as a clinical risk assessment instrument, 2) select cut-point threshold values to define low, moderate, and high risk groups with NS metric.

Area under the ROC curve (AUC) values will be used to determine the overall discriminating ability of NS metric. AUC is an overall performance measurement for the classification of an instrument at various threshold settings, and it tells how much the classifier is capable of distinguishing between classes. The following scale will be used for the evaluation: <0.70=poor,  $\geq 0.70$ =fair,  $\geq 0.80$  good  $\geq 0.9$ =excellent.

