The study will be powered to the least prevalent but most severe condition among potential patients. Based on the allocation ratio of the national rate of prescription opioid use disorder (POUD) among those prescribed opioid medications in the last year, the prevalence of Poud is 2.1%. A sample of approximately 1,523 (32 positive group) achieves 97.68% power to detect a difference of 0.2 between the area under the ROC curve (AUC) under the null hypothesis of 0.5 and the alternative hypothesis of 0.7 using a two-sided z-test at a significance level of 0.050.

The Completer Population (both training and testing set) will be used to assess the overall discrimination ability of NS metric.

*To determine cut-point threshold values for NS total score:*

The objective is to select the optimal cut-points threshold for NS metric to define low, moderate and high risk groups. We will use a hybrid framework where we can make use of the data driven methods to support the clinician's final decision making. Only the training data set will be used in this portion of analysis.

In the first step, the solution space (a subset of optimum choices of cut-point threshold values) will be identified with the following grid search approach: for each pair of risk groups, for example, low risk vs moderate risk, calculate the following performance measurements for each possible cut-point threshold value:

- Sensitivity (SE)

$$SE = \frac{\text{True Positive Rate}}{\text{True Positive Rate} + \text{False Negative Rate}}$$

- Specificity (SP)

$$SP = \frac{\text{True Negative Rate}}{\text{True Negative Rate} + \text{False Positive Rate}}$$

- Positive Predictive Value (PPV): probability that the risk level is present (based on WHO ASSIST) when the result with NS metric is positive.
- Negative Predictive Value (NPV): probability that the risk level is not present (based on WHO ASSIST) when the test result with NS metric is negative.
- Youden's index:

$$\text{Youden's Index} = SE + SP - 1$$

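### The 97.68% power covers only the full-sample AUC; the moderate/high threshold is chosen and then validated with about 16 high-risk patients per half, less precisely than the Protocol and SAP suggest.

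*Protocol*

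**What the plan says.** Protocol 5.1 makes the low, moderate and high risk thresholds the primary objective. Protocol 6.1 justifies the design as giving "a sample of patients with sufficient power to identify and validate clinical threshold values for the NS Metric".

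The sample size calculation is in Protocol 9.2.2 and SAP 3.5, Statistical Aim 1. The SAP states: "A sample of approximately 1,523 (32 positive group) achieves 97.68% power" for an AUC "under the null hypothesis of 0.5 and the alternative hypothesis of 0.7 using a two-sided z-test at a significance level of 0.050". The positive count comes from a national rate of prescription opioid use disorder: "the prevalence of Poud is 2.1" percent.

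The SAP uses different data for different steps:

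- **Overall AUC:** "The Completer Population (both training and testing set) will be used to assess the overall discrimination ability of NS metric".
- **Split:** completers are "randomly split into training data set and testing data set with a 1:1 ratio, stratified by WHO ASSIST risk levels".
- **Choosing cut-points:** "Only the training data set will be used in this portion of analysis". A Youden search gives a set of good candidates, and clinicians pick the final value from it.
- **Validating cut-points (Statistical Aim 2):** the testing half.

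The SAP also gives figures for the halves. Aim 1 assumes sensitivity and specificity of 0.8 and 750 training patients, reports a 95% interval width of 0.143 for sensitivity at the high-risk cut, and calls the intervals narrow. Aim 2 reports 99.8% power for kappa above 0.4 with 750 patients. No repeated split, cross-validation, bootstrap or sensitivity analysis over splits is planned.

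**The concern.** The statement in Protocol 6.1 and the calculation behind it concern different quantities. Showing that an AUC exceeds 0.5 in the full sample says little about how well a particular cut-point is located, or how precisely its sensitivity is known after half the high-risk patients have been set aside. Stratification fixes how many high-risk patients fall in each half, but not which ones.

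At stake are the published moderate/high cut-point and its validated accuracy, both part of the primary result. If they vary a good deal with the random seed, and the stated interval is too narrow, readers will trust them more than the data allow.

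**Working it through.** **1. The plan's power figure.** Inputs from SAP 3.5: 32 positives, 1,523 − 32 = 1,491 negatives, AUC 0.5 against 0.7, two-sided 0.05. Power = Φ((0.20 − 1.96·SE₀)/SE₁). The Hanley-McNeil variance is [A(1−A) + (n₁−1)(Q₁−A²) + (n₀−1)(Q₂−A²)]/(n₁n₀), with Q₁ = A/(2−A) and Q₂ = 2A²/(1+A).

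- SE₀ = 0.0516 and SE₁ = 0.0523, so Φ((0.20 − 0.1011)/0.0523) = Φ(1.89) = 97.1%.
- Obuchowski's simplified variance gives 97.7% and the binormal form 98.7%. The stated 97.68% is reproduced.
- With one half (16 and 745), SE₀ = 0.0730 and SE₁ = 0.0740, giving Φ(0.77) = 78% (binormal form 83%). No AUC test in a half is planned, so this only shows how far the 97.68% depends on all 32 positives.

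**2. High-risk patients per step.** 1,523 × 0.021 = 32.0, so 16.0 per half (750 × 0.021 = 15.75). The 2.1% stands in for the WHO ASSIST high-risk rate, which the documents do not give. An assumed 1% gives about 8 per half, and 4% about 30.

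**3. Interval width for high-risk sensitivity.** With p = 0.8 and n = 16:

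| Method | Full 95% width |
|---|---|
| Wald, 2 × 1.96 × √(0.16/16) | 0.39 |
| Wilson | 0.37 |
| Exact, 13/16 (0.54 to 0.96) | 0.42 |
| Stated in SAP 3.5 | 0.143 |

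The stated 0.143 equals the upper arm alone of an exact 90% interval for 12/15 (0.800 to 0.943). The same reading matches the SAP's other three widths (0.026, 0.056, 0.024). This is an inference, as the SAP does not give the method. The correct width is 2.6 (0.37/0.143) to 2.9 (0.42/0.143) times the stated one. With all 32 patients the exact interval for 26/32 is 0.64 to 0.93.

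**4. Kappa power.** The null is kappa ≤ 0.4 and the alternative only kappa > 0.4. Power needs a specific value; at kappa = 0.4 rejection is about 5%. The 99.8% therefore cannot be checked.

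**5. Dependence on the split.** Simulated normal scores, 32 high-risk and 1,491 others, cut-point at the maximum Youden index. The separation is 1.683 SD (sensitivity = specificity = 0.80) or 0.742 SD (AUC 0.70). Ranges are over repeated runs of at least 400 data sets.

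| Quantity, high-risk cut | SE = SP = 0.80 | AUC 0.70 |
|---|---|---|
| RMSE of Youden index, single split | 0.10–0.11 | 0.12 |
| RMSE, 20 repeats of two-fold cross-validation | 0.07 | 0.08 |
| SD of validated sensitivity, single split | 0.14 | 0.20 |
| SD, halves exchanged and pooled | 0.08–0.09 | 0.12–0.13 |
| Two splits of same data differ by > 0.5 SD | about 20% | about 30% |
| Mean true Youden index, cut from a half | 0.57 | 0.26 |
| Mean true Youden index, cut from full sample | 0.58–0.59 | 0.27 |

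Mapped to the 0–999 scale at AUC 0.70, changing only the split moves the high-risk cut over about 360 to 380 points (5th to 95th percentile). Taking the middle of the top 10% of Youden values leaves 310 to 340. The comparator may be all 1,491 others or only the moderate group, 1,523 × (0.171 − 0.021) = 228; these spans cover both.

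**6. The low/moderate cut.** 1,523 × 0.171 / 2 = 130 moderate or high-risk patients per half. Two splits differ by more than half an SD in only about 2 to 4% (SE = SP = 0.80) or 12 to 15% (AUC 0.70) of data sets.

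**The case against.** Four points on the other side deserve weight.

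- **The SAP does address the halves.** A reader might infer that 97.68% is the only justification offered. It is not: interval widths and a kappa power are given at 750 patients. They do not close the gap, because the width is not a full 95% width and the kappa power has no stated alternative and concerns neither cut-point choice nor sensitivity.
- **A stratified hold-out is legitimate.** A reader might infer that it is biased and should be replaced. The documents do not support that. It was chosen deliberately against overfitting, its estimate was close to unbiased in simulation (within 0.01), and only an untouched test half validates the cut that clinicians actually choose. Resampling validates an automatic rule instead. This stands, and is why resampling belongs beside the hold-out.
- **A different cut is not necessarily a worse one.** The Youden curve is flat near its maximum, and choosing in a half costs only about 0.01 in true Youden index on average. A reader might infer that the single split yields a poor threshold; it does not. The half-SD yardstick is also a convention, not a clinical margin.
- **Not every threshold is affected alike.** A reader might extend the point to both cuts. With about 130 patients per half, the low/moderate cut is much steadier, and the overall AUC is not split at all.

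**Conclusion.** The point holds for the moderate/high cut. The 97.68% does not support a claim of power to identify and validate thresholds, and the SAP overstates the precision of high-risk sensitivity by a factor of 2.6 to 2.9. The loss is mainly in the precision of the validated accuracy and the stability of the cut across splits; average true accuracy falls only slightly. Repeated cross-validation would cut the error of the reported Youden index by about a third without new patients.

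The interval widths rest only on 16 patients and a sensitivity of 0.8. The simulation also assumes normal scores, as the NS metric distribution is not given. Everything scales with the 2.1% proxy. Resampling does not create high-risk patients: even with all 32 the interval stays wide. This should be corrected, but it does not invalidate the design.

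**What to change.** **SAP 3.5, Aims 1 and 2.** Keep the stratified hold-out for the clinician-chosen cut-points. Add a pre-specified repeated stratified two-fold cross-validation (for example 100 repeats), re-running the Youden-maximum rule in every training half. The minimum is to exchange the two halves under that rule and pool the two test results, so that every high-risk patient is validated once. Beside the hold-out result, report sensitivity, specificity, PPV, NPV and kappa, and the spread of selected cut-points across splits. That spread shows dependence on the split and is not a confidence interval.

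**SAP 3.5, precision paragraph.** Restate the high-risk sensitivity width as about 0.37 to 0.42, naming the method, and drop the description of it as narrow. Recheck the other three widths at the same time. State the alternative kappa behind the 99.8%, or remove the figure.

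**Protocol 6.1.** Say that the 97.68% applies to the full-sample AUC against 0.5, and not to identifying or validating thresholds.

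**Cost.** Wording and a few lines of R; no new patients or data. The drawback is that the resampled results, and the exchanged halves with their two different cuts, validate an automatic rule and not the clinicians' final choice. The report must say so.
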